#### 11.2.4 RISK FACTORS FOR REFERRAL FOR MR IMAGING

Risk factors for referral for MRI will be determined by modelling for those patients where mammography and pathology findings do not agree (in terms of tumour presence and extent) whether or not the MRI does agree with the pathology (in terms of tumour presence and extent). This will involve multiple regression analysis of baseline information, including demographic data, history of exogenous hormone consumption and concurrent breast disease, data derived from X-ray mammography, ultrasound and MR imaging, and the cytology and histopathology findings.

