# **2.** AIMS AND OBJECTIVES

The overall aim of this randomised controlled trial is to determine the potential benefits to the patient and to the NHS of the addition of MR imaging to the routine techniques employed for loco-regional staging of primary breast cancer.

The primary objective of the study will be to evaluate the role of MR imaging with respect to:

i) Comparison of the repeat operation or mastectomy rates following primary excision between those planned by conventional triple assessment (clinical examination, X-ray mammography and fine needle aspiration cytology/ core biopsy) and those planned by a combination of triple assessment and dynamic contrast-enhanced MR imaging (DCE-MRI). This will include an economic evaluation from a societal perspective of the cost-effectiveness between the two arms.

The secondary objectives of the study will include:

- i) Determination of the ipsilateral breast tumour recurrence rate for both groups up to five years post-diagnosis.
- ii) Comparison of subsequent chemotherapy/ radiotherapy interventions between women planned by triple assessment and those planned by triple assessment and MR imaging combined.
- iii) An assessment of the quality of life and patient satisfaction with management decisions based on either triple assessment or triple assessment combined with MR imaging.
- iv) An investigation of the risk factors for referral for MR imaging. This will be determined by modelling the different and/or combined approaches to the loco-regional staging of primary breast cancer. This will involve multiple regression analysis of baseline information, including demographic data, history of exogenous hormone consumption and concurrent breast disease, data derived from X-ray mammography, ultrasound and MR imaging, and the cytology and histopathology findings.
- v) Evaluation and comparison of the accuracy of loco-regional staging by X-ray mammography, ultrasound and MR imaging, with reference to the tumour extent determined by histopathology of the resected specimens, in particular with respect to more extensive surgery.
- vi) Observation of the percentage of patients in whom a change in clinical management occurs after MR imaging.

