#### 9.2.4 **RISK FACTORS FOR REFERRAL FOR MR IMAGING**

The risk factors for referral for MR imaging will be determined by modelling the different and/or combined approaches to the loco-regional staging of primary breast cancer.

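### The model of risk factors for MR referral is fitted only where mammography and pathology disagree, so as written it shows when MR succeeds after mammography has failed, not who should be referred

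*Combined protocol and SAP*

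**What the plan says.** Secondary objective iv (section 2) is "An investigation of the risk factors for referral for MR imaging". The Background (section 1) names these risk factors among the issues that a randomised trial must address.

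The endpoint definition in section 9.2.4 is general: the factors are to be "determined by modelling the different and/or combined approaches to the loco-regional staging of primary breast cancer". It fixes no population, outcome or predictor set.

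Section 11.2.4 supplies the detail:

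- **Population:** "modelling for those patients where mammography and pathology findings do not agree", in terms of tumour presence and extent.
- **Outcome:** whether MR agrees with pathology on the same two aspects.
- **Regression data:** the list opens with "multiple regression analysis of baseline information, including demographic data, history of exogenous hormone consumption and concurrent breast disease" and ends with "data derived from X-ray mammography, ultrasound and MR imaging, and the cytology and histopathology findings". Objective iv gives the same list, so it is not a slip confined to one section.

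Three other places bear on the reading. Section 8.6 describes histopathology as work on the excised specimen, sectioned with reference to the MR hard copy. Section 11.2.5 reports false positives, specificity, predictive values and the percentage of inappropriate more extensive surgery in the MRI arm. Section 11.3 plans an exploratory interaction between treatment and breast density.

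**The concern.** A referral rule has to work with what is known before the scan, in every woman who might be scanned. The planned model departs from this in three ways.

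1. **Entry is settled after the decision.** Whether mammography and pathology disagree is known only once the specimen has been examined. At referral nobody can say whether a woman belongs to the modelled group.
2. **Selection removes much of the signal.** MR can help a woman either because mammography is likely to fail in her or because MR is likely to succeed where it fails. Restricting to failures holds the first route fixed and leaves only the second.
3. **One kind of harm is not modelled.** Women in whom mammography was right and MR wrong are excluded, so nothing is learned about who they are.

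The predictor list adds a further problem. MR findings are not available when referral is decided. If MR and specimen pathology are entered as covariates, they also overlap with the outcome, which is built from them.

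At stake is the interpretation of objective iv. A null result for a factor could be read as a reason not to refer on it, when the model was not able to show its effect.

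**Working it through.** **Size of the MR arm.** Section 10.1 gives 1840 patients for 15% versus 10%, 90% power, two-sided 5%, chi-squared without continuity correction. Check:

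n per arm = [1.960·√(2·0.125·0.875) + 1.282·√(0.15·0.85 + 0.10·0.90)]² / 0.05² ≈ 918, or 1836 in total.

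This reproduces the plan's figure closely. With 1:1 allocation (section 6.2) the MR arm has 1840/2 = 920 women. Only they have MR data, so only they can enter the model. The documents give no sample size for the 11.2.4 model itself.

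**How many women the model would use.** The documents give no discordance rate. I take 10% as a low assumption. For the upper range I use the Background's 30 to 63% of women with additional foci despite mammographically suspected uni-focal disease, which is only a proxy.

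| Discordant share (assumed) | Used | Dropped |
|---|---|---|
| 10% | 92 | 828 |
| 30% | 276 | 644 |
| 63% | 580 | 340 |

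**What the model can detect.** For a pre-operative factor X (0 or 1), let d be the probability that mammography disagrees with pathology, and s the probability that MR agrees with pathology given that disagreement. The yield of MR per woman scanned is y = d·s.

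- Planned model: OR = [s₁/(1−s₁)] / [s₀/(1−s₀)]. The term d does not appear.
- Model in all MR-arm women: OR = [y₁/(1−y₁)] / [y₀/(1−y₀)].

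Illustration, all inputs assumed, for a factor other than density with 50% prevalence: d₀ = 20%, d₁ = 50%, s₀ = s₁ = 70%.

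- Yield: 0.20·0.70 = 14% and 0.50·0.70 = 35%.
- OR in all MR-arm women: (0.35/0.65)/(0.14/0.86) = 3.3.
- OR in the planned model: (0.70/0.30)/(0.70/0.30) = 1.0.

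Simulating 920 women 500 times under these inputs gave a median OR of 1.00 (95% range 0.59 to 1.65) for the planned model and 3.32 (2.48 to 4.84) for the model in all MR-arm women.

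**Dependence on s.** With s equal in both groups at 50% or 90%, the all-women OR is 3.0 or 3.7 and the planned OR stays at 1.0. If s differs, the planned model does show an association, but it reflects s alone:

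| s₀ | s₁ | Yield, X=0 | Yield, X=1 | OR, all women | OR, planned |
|---|---|---|---|---|---|
| 70% | 70% | 14% | 35% | 3.3 | 1.0 |
| 50% | 90% | 10% | 45% | (0.45/0.55)/(0.10/0.90) = 7.4 | (0.9/0.1)/(0.5/0.5) = 9.0 |
| 90% | 50% | 18% | 25% | (0.25/0.75)/(0.18/0.82) = 1.5 | (0.5/0.5)/(0.9/0.1) = 0.11 |

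In the last row the factor raises the yield, yet the planned model points the other way.

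**Overlap of predictors with outcome.** In a simplified two-state version (additional disease present or absent), the MR finding used as a predictor within the discordant group gives an AUC of 1.00, because there it determines the outcome. The pre-operative factor gives 0.50. This matters only if MR findings are in fact entered as covariates.

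**The case against.** Several points on the other side have force.

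- **The predictor sentence is loose.** It begins with baseline information. MR and pathology data are needed anyway to construct the outcome, and histopathology could include the pre-operative core biopsy. A reader might infer that the plan certainly regresses the outcome on its own components. The text does not establish that. It does list MR and histopathology within the regression data without separating their roles, so clarification is needed.
- **Density is examined elsewhere.** A reader might infer that the trial would overlook breast density as a reason to refer. Section 11.3 plans a treatment-by-density interaction that is not restricted to discordant women, so that inference fails. It covers one factor only and is exploratory.
- **False positives are not ignored.** Section 11.2.5 reports their overall frequency and the rate of inappropriate more extensive surgery. What is missing is a model of which women are affected.
- **The odds ratio of 1.0 is constructed.** It follows from assuming equal MR success in both groups. It shows what the model can miss, not what it will find.
- **The consequence is limited.** Section 11 is headed as an outline and restricts formal testing to the primary endpoints.

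None of this repairs the population. Section 11.2.4 restricts the model to discordant women, and no section extends it to the others or adds a model of who will be discordant. Dropping the MR and specimen covariates would still leave every estimate conditional on mammographic failure.

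**Conclusion.** The point holds for the model as written. Section 11.2.4 estimates when MR agrees with pathology given that mammography did not. It does not estimate who gains from referral, and it leaves out women whom MR alone would mislead.

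The restriction to discordant women and the reading of the outcome come directly from the text. The sizes do not. The contrast of 3.3 with 1.0 rests on assumed discordance of 20% and 50% and equal MR success of 70%. The count of 92 to 580 women rests on an assumed discordance of 10% to 63%.

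A reader might go further and conclude that the trial cannot inform referral at all, or that its main result is compromised. The documents do not support either conclusion. The planned density interaction and the overall accuracy figures bear on the question, much of the data for a suitable model is in the collection plan, and the primary comparison is untouched. The change should be made because the question is a stated objective and the remedy is cheap.

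**What to change.** Amend section 11.2.4, and the matching list in objective iv, as follows.

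1. **Population:** all MR-arm women with MR and pathology results.
2. **Outcome:** MR corrected the staging given by mammography plus ultrasound (yes/no), with a definition fixed before analysis. Ultrasound belongs in the comparator because every woman has it before entry (section 4.1).
3. **Companion model:** MR wrongly upstaged (yes/no), with the same population and predictors.
4. **Predictors:** only data known before MR, namely demographics, hormone and breast history, density, mammography, ultrasound, and pre-operative cytology or core biopsy. State that MR findings and specimen histopathology serve only to build the outcomes.
5. **Supplementary:** keep the discordant-only model if wanted, labelled as MR performance given mammographic failure.
6. **Interactions:** treat any arm-by-predictor interactions beyond density as supportive only. Power would be limited in a trial sized for a main effect of 15% versus 10%.

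The cost is analysis-plan wording, two outcome definitions and a second model. Patient characteristics, imaging and specimen findings are already collected (sections 8.1 to 8.3 and 8.6). Concurrent breast disease and pre-operative cytology or core biopsy results are not itemised in section 8.1, so confirm that the case report forms hold them; the current list already calls for concurrent breast disease and cytology. One limitation should be stated with the results: pathology is read with the MR hard copy, so the reference standard is not independent of MR.

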#### **11.2.5** Effectiveness of imaging

Correlation of histopathology results with imaging findings will determine the numbers of truepositive, true-negative, false-positive and false-negative cases for mammography, ultrasound and MR imaging, and hence calculation of sensitivity, specificity, accuracy, positive and negative predictive values will be performed. The percentage of inappropriate more extensive surgery will also be reported for the MRI arm.

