#### 8.2 MAMMOGRAPHIC AND ULTRASOUND FINDINGS

The reporting radiologist will record the following information:

- name of radiologist
- background breast pattern on mammography
- location, size and morphological characteristics of all mass lesions, including margin delineation, density, halo and presence of microcalcifications
- presence of stromal deformity, skin changes and pathological nodes
- proximity of tumour to clinically relevant structures
- echo-pattern and presence of acoustic shadowing
- lesion(s) score based on NHS BSP criteria.

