#### 8.3 MR IMAGING FINDINGS

The reporting radiologist will record the following data:

- name of radiologist
- location/ maximum diameter of index lesion
- presence, location and maximum diameter of additional multi-focal and or multi-centric lesions
- proximity of the multi-focal/ multi-centric lesions to the index tumour, skin, chest wall and nipple retro-areolar complex
- outcome of MR imaging, i.e. score for each lesion detected
- date/type of additional biopsy or intervention performed.

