#### 9.2.5 EFFECTIVENESS OF IMAGING

Correlation of histopathology results with imaging findings will be performed with particular reference to:

- detection and classification of lesions
- maximum diameter of all foci of invasive/in situ carcinoma present

- anatomical relationship of multi-centric/multi-focal disease to the index lesion and other structures
- location and extent of additional pathologies.

In addition the inappropriate more extensive surgery\* rates for combined triple assessment and MR imaging will be examined.

\* Inappropriate more extensive surgery is defined as: pre-operative conversion from wide local excision to more extensive surgery (eg quadrantectomy, mastectomy etc) based on triple assessment plus MR imaging, however subsequent histopathological examination of the resected specimen reveals less extensive breast cancer, which could reasonably have been treated by wide local excision alone.

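### Section 11.2.5 only partly answers objective v: it plans counts of correct and incorrect cases, with unit and positivity undefined, and no measure of agreement in tumour size between imaging and histology

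*Combined protocol and SAP*

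**What the plan says.** - **Objective (section 2, secondary objective v).** The accuracy of loco-regional staging by X-ray mammography, ultrasound and MR is to be evaluated and compared "with reference to the tumour extent determined by histopathology of the resected specimens, in particular with respect to more extensive surgery".
- **Endpoint (section 9.2.5).** "Correlation of histopathology results with imaging findings will be performed with particular reference to" four items, one of which is "maximum diameter of all foci of invasive/in situ carcinoma present". The section also defines inappropriate more extensive surgery.
- **Analysis (section 11.2.5).** Matching histopathology to imaging "will determine the numbers of truepositive, true-negative, false-positive and false-negative cases for mammography, ultrasound and MR imaging". From those counts the plan derives the usual rates: sensitivity, specificity, overall accuracy and both predictive values. It adds: "The percentage of inappropriate more extensive surgery will also be reported for the MRI arm".
- **Data.** For mammography and ultrasound the radiologist records "location, size and morphological characteristics of all mass lesions" (section 8.2). For MR the record includes "location/ maximum diameter of index lesion" and the maximum diameter of additional lesions (section 8.3). The pathologist records the size of index and additional lesions (section 8.6).

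No section says whether a case is a woman, a lesion or a breast region, what makes a case positive, or how large a size discrepancy counts as an error. No section plans a mean size difference, limits of agreement, or the share of tumours over- or under-sized.

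**The concern.** The objective is about extent, but the planned statistics are about right and wrong classification. On the natural reading, where a case is positive because a lesion is present and seen, a cancer of 15 mm on histology shown as 45 mm on MR is a true positive. The size error leaves no trace in sensitivity, specificity or the predictive values.

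Extent matters here. Under section 5.2.1(b), a tumour that looks larger on MR than on conventional imaging sends the woman's surgical plan back to the multidisciplinary meeting, with mastectomy a possible result. The Background (section 1) warns about inappropriate mastectomy. Bias in MR size is a plausible route to wider surgery than needed, and undersizing a plausible route to incomplete excision. As written, the trial could report on the accuracy of three modalities without saying how far, or in which direction, each misjudges size.

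The undefined unit is a second gap. Section 4.1 requires proven carcinoma in every woman, so at patient level the index tumour yields no true negatives. Specificity and negative predictive value need a lesion- or region-level unit, which the plan does not give.

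**Working it through.** **1. The plan's own figure.** The only computed design figure is the total of 1840 (section 10.1), which belongs to the primary endpoint. With p1 = 0.15, p2 = 0.10, mean 0.125, two-sided 5% and 90% power, without continuity correction:

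n per arm = [1.960·√(2·0.125·0.875) + 1.2816·√(0.15·0.85 + 0.10·0.90)]² / 0.05² = (0.9167 + 0.5977)² / 0.0025 ≈ 918, or 1836 in total.

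This reproduces 1840. It implies about 920 women in the MRI arm. No figure is given for the imaging analysis.

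**2. Does a presence-based count, or a correlation, show oversizing?** The documents give no tumour sizes, so these inputs are assumptions: histological diameter X lognormal with median 18 mm and log-SD 0.5; imaging diameter Y = b·X·exp(error), error log-SD 0.2; every tumour seen. Then:

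- Mean X = 18·exp(0.5²/2) = 20.4 mm.
- Mean Y = b·18·exp((0.5² + 0.2²)/2) = b·20.8 mm.
- Pearson r = √[(exp(0.25) − 1)/(exp(0.29) − 1)] = √(0.2840/0.3364) = 0.919. The factor b cancels.

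| Imaging | Sensitivity (presence) | r | Mean bias | Oversized by ≥ 10 mm |
|---|---|---|---|---|
| Unbiased (b = 1.0) | 100% | 0.919 | +0.4 mm | 3% |
| 30% too large (b = 1.3) | 100% | 0.919 | +6.7 mm | 23% |
| 50% too large (b = 1.5) | 100% | 0.919 | +10.8 mm | 42% |

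The 100% follows from assuming every tumour is seen, and the constant r from a constant multiplier. The table shows what these two summaries cannot register; it does not predict the trial's results.

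**3. Range over the assumed size.** With the median varied from 12 to 22 mm and b = 1.5, mean bias runs from +7.2 to +13.2 mm, and the share oversized by 10 mm or more from 23% to 52%. The correlation stays at 0.919.

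**4. What the inappropriate-surgery percentage covers.** By the definition in section 9.2.5 it counts women converted before operation to more extensive surgery on triple assessment plus MR, whose histology then shows less extensive disease that could reasonably have been managed by wide local excision. It therefore registers MR overestimation that changed the operation. It does not register oversizing that left the operation unchanged, undersizing, or any error of mammography or ultrasound. It also rests on a judgement of what would have been reasonable.

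**5. Would an agreement analysis be precise enough?** Take up to 920 women and assume the SD of the size difference is 5 to 12 mm. The 95% half-width for mean bias is 1.96·SD/√920 = 0.3 to 0.8 mm. For each limit of agreement it is about 1.96·SD·√(3/920) = 0.6 to 1.3 mm. Fewer evaluable women would widen these, but the existing sample size is ample.

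**The case against.** Four counter-arguments have force.

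- **Objective v is partly served.** A reader might infer that it goes unanswered, or that oversizing can never count against MR. The documents do not support that. The last sentence of section 11.2.5 reports inappropriate more extensive surgery, which is the most harmful result of MR oversizing and speaks directly to the objective's final clause. What stands is that this answer is partial (working, step 4).
- **Positivity is undefined, not defined as presence.** A reader might infer that a grossly oversizing test must score as perfectly accurate. Section 11.2.4 judges mammography and MR against pathology on both presence and extent. A similar rule in 11.2.5 could count the 15 mm versus 45 mm woman as an error. But 11.2.4 serves a different analysis and gives no tolerance, and a yes/no rule would still lose the direction and size of the error.
- **Correlation need not mean a coefficient.** In section 11.2.5 it yields counts, so it must mean case-by-case matching. Section 9.2.5 uses the same word for classification and location. The result on r applies only if someone reads 9.2.5 as calling for a coefficient on diameters.
- **Insensitivity is not favour.** A reader might infer that the plan would rank an oversizing modality higher. The table in step 2 shows equal scores. If the error were instead a constant 3 mm, r = b·s/√(b²s² + 9), where s is the SD of histological size. For s of 6 to 10 mm this gives 0.89 to 0.96 for an unbiased test and 0.97 to 0.99 for one that doubles every size. That reversal depends on the assumed error model and on a coefficient the plan does not name.

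It is also fair that section 11 is headed as an outline, and that section 11 restricts formal testing to the primary endpoints. That limits the weight of the point. It does not supply the missing measure.

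**Conclusion.** The point holds in limited form. Objective v and section 9.2.5 ask about extent and maximum diameter; section 11.2.5 plans no measure of agreement in size and leaves unit and positivity undefined. On a presence-based reading, or with a correlation coefficient, systematic sizing error would not show. Under the assumed size distribution, a mean bias of about +7 to +13 mm (50% oversizing, median 12 to 22 mm) would leave both summaries unchanged. The inappropriate-surgery percentage recovers part of the question, for MR only.

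The millimetre figures rest on assumed sizes and errors. The absence of a size-agreement measure rests on the text alone. This is a cheap improvement to a secondary, descriptive endpoint. The primary analysis and the total of 1840 are unaffected.

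**What to change.** In section 11.2.5:

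1. Keep the 2×2 analysis for detection of both index and additional lesions, since section 9.2.5 lists detection. State the unit (woman, lesion or region) and what makes a case positive on imaging and on histology.
2. Add, for each modality, the mean difference (imaging minus histology) in maximum diameter with 95% limits of agreement. Use the log scale if the spread grows with size, otherwise mm. Report separately the percentages over-sized and under-sized by a pre-stated margin.
3. Compare modalities within woman in the MRI arm, among women with a recorded size on each modality, and report how many are left out and why.
4. Report separately, or exclude, women converted to primary chemotherapy (an option listed in section 8.4), because specimen size may no longer reflect size at imaging.
5. Keep the percentage of inappropriate more extensive surgery as planned.

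**Cost.** Wording plus a short analysis of sizes that sections 8.2, 8.3 and 8.6 already collect. One margin must be agreed before the data are examined. Section 8.2 asks for the size of mass lesions rather than maximum diameter by name, so the form should be checked to confirm that a comparable dimension is recorded. Women without a measurable lesion on a modality drop out of that comparison, which should therefore be read beside the detection results.
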